5.4.2. Study CBP-201AU002

A follow-on study (Protocol CBP-201AU002) entitled: “A Randomized, Double-Blind, Placebo-Controlled, Multiple Ascending Dose Study of the Safety, Pharmacokinetics and Preliminary Efficacy of CBP-201 in Patients with Moderate to Severe Atopic Dermatitis” has been completed (Clinical Study Report is still in the process of development) at the time of this protocol. This study is a 12-week, double-blind, randomized, placebo-controlled, multi-center, multi-national, multiple ascending dose (MAD) study to assess the safety, PK profile and preliminary efficacy of treatment with CBP-201 in subjects with moderate to severe AD. The primary objective of this study was to assess the safety and tolerability of multiple subcutaneous (SC) doses of CBP-201 in patients with moderate to severe AD.

This study was conducted at 9 study sites in Australia and 4 in New Zealand. Subjects were randomized in a 4:1 ratio to receive CBP-201 or placebo once a week for 4 doses, with approximately 10 patients (8 active:2 placebo) randomized in each dose cohort. Three ascending dose levels were planned (75, 150 and 300 mg CBP-201). All dose escalations were subject to Safety Review Committee blinded review. The treatment period was 4 weeks in duration. Subjects were followed for an additional 8 weeks for safety, efficacy and to further characterize the PK and PD profile of CBP-201.

A total of 86 subjects were screened and 32 subjects with moderate to severe AD (ages 20 – 65) were enrolled and randomized with 31 completing the study and one subject who was withdrawn from the study on Day 1 following randomization but prior to dosing. The study results are listed as following:

Efficacy: Administration of CBP-201 for 4 weeks resulted in rapid improvements in EASI, IGA, and Pruritis Numeric Rating Scale (P-NRS) at all doses above the lowest dose (75 mg). On Day 29, 87.5% (7/8) of patients in the 150mg group had a 50% reduction in the EASI score (EASI-50) while 100% (7/7) of patients in the 300 mg group achieved EASI-50 versus 37.5% (3/8) in the placebo group. For IGA, 50.0% (4/8) of patients in the 150 mg group, 42.9% (3/7) of patients in the 300 mg group, and only 12.5% (1/8) in the placebo group had an IGA score of 0 to 1 (clear, almost clear). Average weekly P-NRS in severity decreased by 41.0% in the CBP-201

150 mg group, by 52.8% in the 300 mg group versus 22.8% in the placebo group. P-NRS response rates (>3-point decrease) were greater for the 150 mg (50%, 4/8) and 300 mg groups (57%, 4/7) versus the placebo group (25%, 2/8) on Day 29.

Safety: CBP-201 appeared to be safe and well-tolerated when administered to male and female adult patients with moderate to severe AD, at SC doses of 75 mg, 150 mg, and 300 mg. These conclusions were based on the following findings from 23 patients in the pooled CBP-201 group who received at least one dose of CBP-201 and 8 of 8 patients in the placebo group.

- There were no SAEs, life-threatening TEAEs, or deaths reported on study.
- There were no TEAEs leading to the discontinuation from the study.
- The majority of TEAEs were mild. The number and severity of TEAEs and treatment related TEAEs did not increase with increasing CBP-201 dose level. Of 51 TEAEs reported across the pooled CBP-201 group, 9 events were deemed by the Investigator to be related to study drug, and 3 of 11 TEAEs in the placebo group were deemed related to placebo treatment. There was no treatment related severe TEAEs reported.
- The most common Adverse Events (AE) during the study were exacerbation of AD (26.1% in the combined CBP-201 group and 37.5% in placebo group), headache, and upper respiratory tract infection.
- By dose across the CBP-201 treatment groups, there were no apparent differences between the different dosing groups in terms of study treatment related TEAEs.
- There were no clinically significant injection site reactions that were reported as AEs
- There were no clinically significant and/or study drug-related changes in vital signs, ECG parameters, or physical examination findings.
- Immunogenicity assay results showed 5 of 23 patients (21.7%) had a treatment-induced positive response for ADA with very low titration. Overall, the immunogenicity of CBP 201 varied inversely with the CBP-201 dose, with the incidence of treatment-induced ADA positive response observed to decrease with greater CBP 201 doses.

Pharmacokinetic: The highest CBP-201 concentrations were observed approximately one week (Day 29) after the fourth CBP-201 administration on Day 22. The median $t_{1/2}$ was approximately 10 days for the CPB-201 150 mg to 300 mg groups. Dose proportionality assessed based on AUC_{0-t} and C_{max} , showed that an increase in exposure was greater than proportional as the dose increased from 75 mg to 150 mg, and proportional when the dose increased from 150 mg to 300 mg.

Pharmacodynamics: CBP-201 at the 150 mg and 300 mg doses resulted in a steady decline of serum TARC and LDH.

5.5. Study Rationale

CBP-201 is a recombinant monoclonal antibody that binds human interleukin-4 receptor alpha (IL-4R α), a common subunit of the interleukin 4 (IL-4) and interleukin 13 (IL-13) receptor dimers. CBP-201 blocks signaling from both IL-4 and IL-13 which are thought to play a role in the pathogenesis of atopic dermatitis (AD). CBP-201 is administered as a subcutaneous (SC) injection. This study is designed to test various CBP-201 dosing regimens over an extended period in subjects with AD.

6. STUDY OBJECTIVES

6.1. Primary Objective

Assess the efficacy of various treatment regimens of CBP-201 in subjects with moderate to severe AD.

6.2. Secondary Objectives

In subjects with moderate to severe AD:

- Assess the safety and tolerability of various treatment regimens for CBP-201
- Characterize the steady-state pharmacokinetic (PK) profile of various treatment regimens for CBP-201

6.3. Exploratory Objectives

Exploratory objectives of the study are: In subjects with moderate to severe AD:

- Characterize the pharmacodynamic (PD) profile of various treatment regimens for CBP-201
- Characterize the PD/efficacy relationship of various treatment regimens for CBP-201

7. INVESTIGATIONAL PLAN

7.1. Overall Study Design and Plan

This is a randomized, double-blind, placebo-controlled study to assess the efficacy, safety, PD and PK profile of CBP-201 administered to eligible adult subjects with moderate to severe AD. The study period includes a treatment period of 16 weeks and a follow-up period of 8 weeks.

Subjects will be randomized 1:1:1:1 into one of the following 4 dosing regimen groups (Table 2):

- CBP-201: 600 mg (4 vials) on D1, 1 vial of CBP-201 and 1 vial of placebo on W2 and the same dose Q2W thereafter through W16. Total CBP-201 dose over 16 weeks: 1800 mg.
- CBP-201: 600 mg (4 vials) on D1, CBP-201 300 mg (2 vials) on W2 and Q2W thereafter through W16. Total CBP-201 dose over 16 weeks: 3000 mg.
- CBP-201 600 mg (4 vials) on D1, placebo (2 vials) on W2, CBP-201 300 mg (2 vials) on W4, W8, W12 and W16, alternating with placebo (2 vials) on W6, 10, and 14. Total CBP-201 dose over 16 weeks: 1800 mg.
- Placebo only: 4 vials on D1, 2 vials on W2 and Q2W thereafter through W16.

Table 2. Subcutaneous Injection Schedule Through Week 16

CBP-201 or Placebo Treatment Regimen	D1	D15/W2	D29/W4	D43/W6	D57/W8	D71/W10	D85/W12	D99/W14	D113/W16	# Vials over 16 weeks
	Number of vials: C = CBP-201 vs. P = placebo									
600 mg load D1 then 150 mg Q2W	4xC	1xC / 1xP	1xC / 1xP	1xC / 1xP	1xC / 1xP	1xC / 1xP	1xC / 1xP	1xC / 1xP	1xC / 1xP	12xC / 8xP
600 mg load D1 then 300 mg Q2W	4xC	2xC	2xC	2xC	2xC	2xC	2xC	2xC	2xC	20xC / 0xP
600 mg load D1 then 300 mg Q4W	4xC	2xP	2xC	2xP	2xC	2xP	2xC	2xP	2xC	12xC / 8xP
placebo	4xP	2xP	2xP	2xP	2xP	2xP	2xP	2xP	2xP	20xP

Note: C = CBP-201; P = placebo; #x = # vials.

Using sterile technique, for the CBP-201 300 mg dose, 1 mL is to be withdrawn from each of 2 vials to result in approximately 300 mg CBP-201, and for 600 mg, 1 mL is to be withdrawn from each of 4 vials to result in approximately 600 mg. Similarly, for the placebo dose, 1 mL is to be withdrawn from each of 2 vials to result in the equivalent volume to the 300 mg CBP-201 dose, and for 600 mg, 1 mL is withdrawn from each of 4 vials. For the 150 mg CBP-201 dose, in order to maintain the blind, 1 mL is to be withdrawn from each of a CBP-201 vial and a placebo vial to deliver the same volume as a 300 mg CBP-201 dose.

7.1.1. Screening Period (Day -45 [D-45] to D-1):

After providing informed consent, subjects will be assessed for study eligibility at an initial screening visit within 45 days before the baseline visit. Medical history, physical examination

(including height and weight), concomitant medication review, clinical laboratory tests, including tests for HIV and hepatitis, and a 12-lead ECG will be obtained during this period. A blood pregnancy test will be obtained for all women of child-bearing potential.

See [Table 1](#) for details on the procedures to be completed during Screening.

Subjects will also be instructed to apply a bland emollient twice a day to affected areas for the duration of the study (investigators are free to recommend the preferred bland emollient for subject use and the cost will be reimbursed by the Sponsor). To allow for assessment of dryness and scaling, emollients should be avoided during the 4 hours prior to evaluation. All screening laboratory tests must be reviewed by study staff prior to Baseline (D1) to confirm eligibility.

AD severity and impact will be assessed as follows:

By the subject:

- Peak Pruritus Numerical Rating Scale (PP-NRS): a single self-reported item designed to measure peak pruritus or ‘worst’ itch, over the previous 24 h based on the following question: ‘on a scale of 0 to 10, with 0 being “no itch” and 10 being “worst itch imaginable”, how would you rate your itch at the worst moment during the previous 24 hours?’ ([37](#)). See [Section 16.1, Appendix A](#). The PP-NRS (daily itch diary) will be distributed at start of Screening and will be reviewed by study staff at the Baseline Visit (D1). Instruct the subject to complete the daily PP-NRS (daily itch diary) for the 7 days prior to the Baseline Visit to calculate the subjects’ baseline average score. Subsequently, the daily PP-NRS will be captured for each day (24 hours previous).
- Dermatology Life Quality Index (DLQI): a 10-item questionnaire assessing the impact of AD on quality of life (QOL) over the past week, with an overall scoring of 0 (absent disease) to 30 (severe disease); higher scores indicative of poorer QOL. See [Section 16.2, Appendix B](#).
- Patient Oriented Eczema Measure (POEM): a 7-item questionnaire assessing disease symptoms on a 0 to 4 scale (dryness, itching, flaking, cracking, sleep loss, bleeding and weeping) with a scoring system of 0 (absent disease) to 28 (severe disease); higher scores indicative of poorer quality of life. See [Section 16.3, Appendix C](#).

By the Investigator:

- Investigators Global Assessment (IGA): Validated Investigator Global Assessment for Atopic Dermatitis (vIGA-AD™) scale is a 5-point categorical scale (0 = clear; 1 = almost clear; 2 = mild; 3 = moderate; 4 = severe) based on the overall appearance of the lesions at a given time point. Note that to qualify for eligibility, the IGA score must be ≥ 3 . See [Section 16.4, Appendix D](#). Note also that IGA-1 should not include scaling or induration. To allow for assessment of dryness and scaling, emollients should be avoided during the 4 hours prior to evaluation.

- Eczema Area and Severity Index (EASI): EASI score measures the severity and extent of AD and erythema, infiltration, excoriation and lichenification on 4 anatomic regions of the body: head/neck, trunk, upper and lower extremities. The total EASI score ranges from 0 (minimum) to 72 (maximum) points; higher scores reflecting the worse severity of AD. Note that to qualify for eligibility, the EASI score must be ≥ 16 . See [Section 16.5, Appendix E](#).
- Percent body surface area (BSA) of AD involvement with maximum percentages for each region using the “rule of nines”: head and neck [9%], anterior trunk [18%], back [18%], upper limbs [18%], lower limbs [36%], and genitals [1%]. The number of handprints of AD skin in a body region can be used to determine the extent (%) to which a body region is involved with AD. The area represented by the palmar surface of the subject's hand with all five digits adducted together, is approximately 1% of the subject's BSA, regardless of the subject's age. Handprints across various body regions assessed is used to calculate BSA % of AD involvement. Note that to qualify for eligibility, the BSA % score for AD involvement must be ≥ 10 . See [Section 16.6, Appendix F](#).
- Severity scoring of AD (SCORAD): a clinical tool for assessing the severity (extent/intensity) of AD and subjective signs/symptoms (e.g. pruritus/insomnia). The extent of lesions is scored by applying the rule of nines. The intensity is determined by grading each of the 6 items on a scale from 0 to 3 (erythema, edema, oozing/crusting, excoriations, lichenification and dryness). Each item is be scored on the most representative area for a given intensity item. See [Section 16.7, Appendix G](#). To allow for assessment of dryness and scaling, emollients should be avoided during the 4 hours prior to evaluation.

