10.5.1.2. Secondary Efficacy Endpoints

Comparing each CBP-201 regimen to placebo:

- IGA (0-1): Proportion of subjects with both IGA score 0 to 1 (clear; almost clear) and a reduction of ≥ 2 points at Week 16
- EASI:
 - EASI-50: Proportion of subjects achieving $\geq 50\%$ reduction of EASI score from baseline at Week 16
 - EASI-75: Proportion of subjects achieving $\geq 75\%$ reduction of EASI score from baseline at Week 16
 - EASI-90: Proportion of subjects achieving $\geq 90\%$ reduction of EASI score from baseline at Week 16
- Change from Baseline to W16 in weekly average PP-NRS
- Number of AD flares from baseline through Week 16
- Number of days with AD flare through Week 16

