| | If "No", over the last week how much has your skin been a problem at work or studying ? | A lot
A little
Not at all | 

 |

16.3. APPENDIX C (POEM):

PATIENT ORIENTED ECZEMA MEASURE (POEM)

Patient-Oriented Eczema Measure					
Please circle one response for each of the seven questions below. Young children should complete the questionnaire with the help of their parents. Please leave blank any questions you feel unable to answer.					
1. Over the last week, on how many days has your/your child's skin been itchy because of the eczema?					
No Days	1-2 Days	3-4 Days	5-6 Days	Every Day	
2. Over the last week, on how many nights has your/your child's sleep been disturbed because of the eczema?					
No Days	1-2 Days	3-4 Days	5-6 Days	Every Day	
3. Over the last week, on how many days has your/your child's skin been bleeding because of the eczema?					
No Days	1-2 Days	3-4 Days	5-6 Days	Every Day	
4. Over the last week, on how many days has your/your child's skin been weeping or oozing clear fluid because of the eczema?					
No Days	1-2 Days	3-4 Days	5-6 Days	Every Day	
5. Over the last week, on how many days has your/your child's skin been cracked because of the eczema?					
No Days	1-2 Days	3-4 Days	5-6 Days	Every Day	
6. Over the last week, on how many days has your/your child's skin been flaking off because of the eczema?					
No Days	1-2 Days	3-4 Days	5-6 Days	Every Day	
7. Over the last week, on how many days has your/your child's skin felt dry or rough because of the eczema?					
No Days	1-2 Days	3-4 Days	5-6 Days	Every Day	
Total Score (maximum 28) _____					

Responses are scored as follows:

- No days = 0
- 1-2 days = 1
- 3-4 days = 2
- 5-6 days = 3
- Every day = 4

16.4. APPENDIX D (IGA):

Validated Investigator Global Assessment scale for Atopic Dermatitis

vIGA-AD™

Instructions:

The IGA score is selected using the descriptors below that best describe the overall appearance of the lesions at a given time point. It is not necessary that all characteristics under Morphological Description be present.

Score	Morphological Description
0 – Clear	No inflammatory signs of atopic dermatitis (no erythema, no induration/papulation, no lichenification, no oozing/crusting). Post-inflammatory hyperpigmentation and/or hypopigmentation may be present.

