1 – Almost clear	Barely perceptible erythema, barely perceptible induration/papulation, and/or minimal lichenification. No oozing or crusting.
2 – Mild	Slight but definite erythema (pink), slight but definite induration/papulation, and/or slight but definite lichenification. No oozing or crusting.
3 – Moderate	Clearly perceptible erythema (dull red), clearly perceptible induration/papulation, and/or clearly perceptible lichenification. Oozing and crusting may be present.
4 – Severe	Marked erythema (deep or bright red), marked induration/papulation, and/or marked lichenification. Disease is widespread in extent. Oozing or crusting may be present.

Notes:

1. In indeterminate cases, please use extent to differentiate between scores.

For example:

- Patient with marked erythema (deep or bright red), marked papulation and/or marked lichenification that is limited in extent, will be considered “3 – Moderate”.

2. Excoriations should not be considered when assessing disease severity.

Copyright ©2017 Eli Lilly and Company – Used with the permission of Eli Lilly and Company under a Creative Commons Attribution-NoDerivatives 4.0 International License - <https://creativecommons.org/licenses/by-nd/4.0/>

16.5. APPENDIX E (EASI):

ECZEMA AREA AND SEVERITY INDEX (EASI)

EASI score measures the severity and extent of AD and erythema, infiltration, excoriation and lichenification on 4 anatomic regions of the body: head/neck, trunk, upper and lower extremities. The total EASI score ranges from 0 (minimum) to 72 (maximum) points; higher scores reflecting the worse severity of AD.

How to Use EASI

The EASI scoring system uses a **defined process** to grade the **severity of the signs** of eczema and the **extent affected**:

1. Select a body region

Four body regions are considered separately:

- Head and neck
- Trunk (including the genital area)
- Upper extremities
- Lower Extremities (including the buttocks)

2. Assess the extent of eczema in that body region

Each body region has potentially 100% involvement. Using the table below, give each respective body region a score of **between 0 and 6** based on the percentage involvement. Precise measurements are not required.

% involvement	0	1-9%	10 - 29%	30 - 49%	50 - 69%	70 - 89%	90 - 100%
Region score	0	1	2	3	4	5	6

To aid in your body region grading you can use the **diagrams** in [Appendix 1](#).

3. Assess the severity of each of the four signs in that body region:

1. Erythema
2. Edema/papulation
3. Excoriation

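### Protocol 7.1.1 says an IGA score of 1 should exclude induration, but the vIGA-AD scale in Appendix D allows it, so the IGA 0–1 responder cut can be read two ways

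*Protocol*

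**What the plan says.** Protocol 7.1.1, in the bullet on the investigator's IGA, names the vIGA-AD five-point scale, points to Appendix D, and adds: "Note also that IGA-1 should not include scaling or induration".

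Appendix D prints the scale. The relevant descriptors are:

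- Score 0: "No inflammatory signs of atopic dermatitis (no erythema, no induration/papulation, no lichenification, no oozing/crusting".
- Score 1: "Barely perceptible erythema, barely perceptible induration/papulation, and/or minimal lichenification. No oozing or crusting".
- Score 2: "Slight but definite erythema (pink), slight but definite induration/papulation, and/or slight but definite lichenification".
- General instruction: "It is not necessary that all characteristics under Morphological Description be present".

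Scaling appears in none of the five descriptors.

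Protocol 10.3 refers the reader to 7.1.1 for the details of the AD assessments, and the visit sections repeat the IGA through Week 16. The first-listed secondary endpoint (Protocol 10.5.1.2) is: "Proportion of subjects with both IGA score 0 to 1 (clear; almost clear) and a reduction of ≥ 2 points at Week 16". Protocol 10.5.1.3 adds, among the other endpoints, the proportion improving by at least 2 IGA points.

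SAP section 8.A describes vIGA-AD by its five labels only. SAP section 8.C reports pairwise p-values for IGA response as exploratory.

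**The concern.** The protocol gives raters two definitions of score 1 that disagree on induration. The note has no effect at entry, where IGA must be at least 3. It can matter only after baseline, at the line between 1 and 2, and that line is the responder cut for IGA 0–1.

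Two things are at stake. First, raters at different sites could score the same skin differently, so the endpoint might not mean the same thing across about 60 sites. Second, if the note is followed, the result is no longer a response on the vIGA-AD scale as printed, because the note removes one permitted feature of score 1 and brings in a sign that the scale does not grade.

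**Working it through.** No figure in the plan is in dispute, so the check is mainly a comparison of texts. Below, faint induration means induration at the barely perceptible level.

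**1. Can the two texts be read together?** Take a subject whose only residual sign is faint induration.

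- Score 0 is excluded under both texts, because it requires no induration or papulation.
- Score 1 fits Appendix D. The instruction that not every characteristic need be present makes induration optional at score 1. The note says it should be absent. Optional and absent are different rules.
- Score 2 calls for signs that are slight but definite, which faint induration is not.

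Under Appendix D the score is 1. Under the note no score fits. A rater who takes the note seriously could move to 2, the next score up, although the descriptor for 2 is not met.

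**2. Does another passage settle it?** Inclusion criterion 1(b)(i) points to Appendix D, the synopsis describes vIGA-AD without the note, and SAP 8.A names vIGA-AD without modification. None of these says which text prevails. Section 7.1.1 itself cites Appendix D and still adds the note.

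**3. Effect on the endpoints.** Baseline IGA must be 3 or 4, so any score of 0 or 1 is already a drop of at least 2 points. The 1-versus-2 line alone therefore decides IGA 0–1 response.

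| Baseline IGA | Week 16 score | Drop | IGA 0–1 response | Improvement of 2 points or more |
|---|---|---|---|---|
| 3 | 1 (Appendix D) | 2 | yes | yes |
| 3 | 2 (possible under the note) | 1 | no | no |
| 4 | 1 (Appendix D) | 3 | yes | yes |
| 4 | 2 (possible under the note) | 2 | no | yes |

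**4. Size per subject.** With 55 randomized per arm and missing values counted as non-response, one re-scored subject changes an arm's rate by 1/55 = 1.8 percentage points. Only subjects with an observed Week 16 score and no earlier rescue can be affected. The SAP already counts the others as non-responders.

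**5. Direction.** Let p_A and p_P be the active and placebo rates under Appendix D, and let f be the share of responders re-scored, assumed equal in the two arms. The difference becomes

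(1 − f)·p_A − (1 − f)·p_P = (1 − f)(p_A − p_P),

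so it shrinks toward zero. As an illustration, assume 40% versus 10%; neither rate is a planning figure in the documents. The difference is 30 points at f = 0, 27 at f = 10%, 21 at f = 30% and 15 at f = 50%. The documents give no value for f, so this shows direction and proportionality only.

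**The case against.** The strongest reply is that little depends on this endpoint. Protocol 13.5.5 and SAP 5.A limit formal comparison to the primary endpoint, Protocol 13.6.2 plans no formal comparison for secondary endpoints, and the gatekeeping covers EASI percentage reduction only. Being listed first gives IGA 0–1 no rank in testing. That stands, and it limits the severity.

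It can also be said that the plan clearly means vIGA-AD to govern, and that Appendix D asks for the descriptors that best describe the overall appearance. This makes the intent clearer but does not withdraw the note.

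A reader might infer more than the documents support:

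- **A known, large loss of responders.** One could assume 40% response, 80% of it at score 1 and 25% to 75% of those with faint induration, giving 0.40 × 0.80 × 0.25 = 8 points up to 0.40 × 0.80 × 0.75 = 24 points. The 80% and the 25% to 75% have no source in the documents. The 40% could lean only on 3/7 and 4/8 subjects at Day 29 of a weekly-dosing study (Protocol 5.4.2). The product also requires every site to follow the note.
- **A forced score of 2 at all sites.** The note says should, not must, and assigns no score. Rater training and case report forms are not visible here. Sites could differ; whether they did is unknown.
- **A bias in favor of active treatment.** Raters are blinded, so which text a rater follows is unrelated to arm. The expected effect is dilution.

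**Conclusion.** The inconsistency is real and sits in current protocol text. It leaves the IGA 0–1 cut open to two readings and, for subjects entering at IGA 3, the 2-point improvement endpoint as well. The supported size is 1.8 percentage points per re-scored subject, assuming 55 analyzed per arm. The total effect cannot be estimated from the documents, because they do not say how many subjects would have faint induration at Week 16 or which text raters followed.

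The expected direction is a smaller treatment difference. That rests on blinded scoring and on a similar share of responders being affected in each arm.

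The primary EASI analysis, eligibility and stated power do not depend on this point. Severity is moderate: a secondary endpoint definition needs reconciling, and the trial's main conclusion is not threatened.

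**What to change.** Delete the sentence on IGA-1 from Protocol 7.1.1. State there that IGA is scored only by the Appendix D vIGA-AD descriptors at every visit, and send sites a short clarification. The emollient instruction in the same bullet can stay, since SCORAD grades dryness. The cost is one protocol sentence and one site notice, with no new assessments or subjects.

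Whether this can still influence scoring is not clear: the SAP is dated 15 October 2021 and rests on a protocol amendment of 28 May 2020. If Week 16 scoring is complete, disclose the conflict wherever IGA 0–1 is reported, and use the by-center summaries of secondary endpoints already planned in SAP 5.D to look for site differences. Those summaries can show only gross differences: 220 subjects over about 60 sites is about 3.7 per site, or about 0.9 per arm per site.

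An analysis with and without the sites that applied the note is not recommended, because the plan collects no record of which rule a rater used.
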